During the study, women must agree not to change medications known to have sexual side-effects unless mandated by their physician (medication use data will be collected at each assessment point). Participants will be encouraged to limit/eliminate internet use as a source of additional information about sexual dysfunction during the trial (and asked about this at post-treatment). We have found this request feasible in past^{9,87} research. Every 3 months, we will analyze recruitment for group differences in ethno-cultural categories and sexual orientation, and adjust recruitment efforts to ensure that our sample reflects cultural and sexual diversity of the population of Canada and the United States, and is balanced across arms. The coordinator gathering data will not be involved in administering or navigating treatment. To minimize inter-navigator variation, navigators will receive training from [name], CoA [name], and [name]. Specifically, each navigator will receive a reading list of readings relevant to treatment of women's sexual concerns. Navigator-related measures will be evaluated for potential effects on outcomes and controlled for.

[figure not shown]
Navigator related measures include:

1. Empathy subscale of the Barrett-Lennard Relationship Inventory, a valid measure of perceived provider empathy that predicts outcomes in CBT (this was already uploaded in Rise).
2. Perceived navigator effectiveness with the Working Alliance Inventory, Short Form (this was already uploaded in Rise).
3. In addition, each navigator will keep track of the number of minutes spent with each participant over the course of the 8 modules, and this number will also be used as a moderator.

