Assessment points: CONSORT²⁸ guidelines will be followed in terms of tracking number of participants recruited, randomized, and retained through assessment and treatment. For CBT-O and MBT-O groups, there are 3 assessment points (baseline; post-treatment (within 2wks of completing the 8-module program); and 6-month follow-up). For the wait-list group, there are 2 pre-treatment assessments at waiting period start and after randomization to treatment (4 assessment points; same online questionnaires). No treatment will be given to wait-list participants during this waiting period. However, after the second online questionnaires are complete, they will be randomized to either the CBT-O or MBT-O arm of eSense. All participants will also be sent a mid-treatment link to an online question that asks them to write freely about their reactions to the treatment to date. This is included to examine quality assurance of the intervention. To minimize attrition, honoraria will be linked to completion of each assessment point: \$30 for (each) baseline assessment, and \$40 at post-treatment and 6-month follow-up assessment points.

Protocol: All participation will be remote, requiring no in-person meetings. Prospective participants will contact the study coordinator at UBC via e-mail, then set up a phone screen for inclusion/exclusion criteria (Fig 1). Consent forms will be sent to prospective participants prior to the scheduled phone screen by the study coordinator. Women will be informed of the length of the intervention (8 modules; 8-12 wks), expectations for homework (1-2 hours/week), and the use of treatment navigators. After meeting the screening criteria, the study coordinator will send prospective participants a personalized link to a Qualtrics questionnaire battery. The first page of the questionnaires will be the e-consent form. Participants must read and electronically sign the consent form before they move on to the baseline questionnaires. The e-consent form will indicate that any questions/issues they raise in interactions with study staff that are worrisome (e.g., suicidal ideation) will automatically prompt the coordinator to contact them. Women who choose not to participate will be provided with other resources (websites, directories of sex therapists, books).

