Prior to beginning eSense (Fig 1), participants will have an initial 15-30 min conversation via zoom with their assigned navigator, who will explain their role. These regularly scheduled⁶⁴ meetings have been found to significantly increase participation rates.^{83,93} Once treatment begins, navigators will schedule weekly 15-20 min sessions, and these will follow a structured outline that includes: 2-3 min general introduction, 10-15 min to check in on any concerns arising during completion of assigned homework, and 2-3 min to close and schedule their next session. Either the participant or the navigator can request a reassignment if there is not a good “fit.” This can happen at any time during the study by informing the study coordinator. Navigators will be: undergraduate psychology students; GPA>3.5; coursework in research methods, clinical psychology or human sexuality; and available to complete training (see letter of support from UBC Psychology chair, **Appendix**). They must be able to commit at least a full year to the project. Navigators will be asked to electronically sign the consent form. These signed consent forms will be stored securely on MS OneDrive. Only the study coordinator and co-investigators will have access

to the consent forms and it will not be stored with other data. Each navigator will be assigned a participant to work through all 8 modules. Navigators will be assigned up to 4 participants at the same time. Navigators can choose to be involved with either CBT-O or MBT-O, or both arms, if they feel comfortable. Their feedback to participants will largely be the same regardless of which arm the participant is in. A new coded variable will be included in the analysis to examine whether a navigator was assigned to an arm based on their preference (1) or no preference (0). Students will be interviewed by [name] to assess comfort with discussing sexual issues, interpersonal skills and ability for empathic listening. Potential impact of navigators will be assessed statistically prior to the main analyses and controlled for. CoA [name] will oversee navigator supervision.

We may conduct an exit interview for trans participants and participants who are not exclusively heterosexual so we can receive feedback on how our program could be improved for sexual orientation, gender, and sex-inclusivity. This exit interview would be optional for participants.

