2° outcomes: Treatment satisfaction will be assessed with (i) two face-valid single item measures measured on through the eSense platform at the beginning of modules 2-8 and measures via Qualtrics a week after completing module 8 asking participants to rate helpfulness of content covered in the previous module, and ease of reading the content (1-10 scale); Research suggests a cut-off of 6.5/10 on these measures to indicate acceptable utility and clarity of content⁹⁴; (ii) qualitative feedback about website and homework assignments collected by treatment navigators; (iii) adapted Erectile Dysfunction Inventory of Treatment Satisfaction,⁹⁵ a widely used scale measuring satisfaction after treatment for erectile dysfunction. Perceived relationship with navigators is assessed at post-treatment with two measures: (i) Empathy subscale of the Barrett-Lennard Relationship Inventory,⁹⁶ a valid measure of perceived provider empathy that predicts outcomes in CBT⁹⁷; (ii) perceived navigator effectiveness with the Working Alliance Inventory, Short Form.⁹⁸ Treatment compliance will be measured by: (i) recording number of weeks and treatment sections completed⁹⁹; (ii) eSense website engagement and performance by Google analytics (e.g., page views, # visits/sessions, page views/visit, visit duration, unique/returning users); these metrics are recommended by the E-CONSORT guidelines as important for e-health intervention studies. The platform used to house eSense tracks views of a page and completion of the overall program, enhancing and complementing what analytics can provide; (iii) navigators will ask participants to rate homework completion on a Likert scale ranging from “did not attempt” to “successfully completed all assignments” weekly; (iv) having participants complete the Homework Rating Scale-II (HRS-II)¹⁰⁰ at the beginning of modules 2-8 on the eSense platform and then complete it again week via Qualtrics after completing module 8 to provide a comprehensive measure of experience with the homework; (v) measuring navigator adherence to study guidelines by coding a random 20% of Zoom sessions (participants will be informed of these recordings) for adherence (to be done by [name]’s trainee; no funding requested), using a previous adherence scale we have used.^{17,81} Sexual function will be measured using the total score of the Female Sexual Function Index,⁹¹ a validated self-report measure of sexual function.

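### Navigator empathy and alliance are rated only after the primary change is complete, so the plan cannot tell a navigator effect on improvement from an effect of improvement on the rating

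*Combined protocol and SAP*

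**What the plan says.** The section on protecting against sources of bias (after 2.3) states that "Navigator-related measures will be evaluated for potential effects on outcomes and controlled for". It lists three measures: "Empathy subscale of the Barrett-Lennard Relationship Inventory, a valid measure of perceived provider empathy that predicts outcomes in CBT"; "Perceived navigator effectiveness with the Working Alliance Inventory, Short Form"; and a time log, in which "each navigator will keep track of the number of minutes spent with each participant over the course of the 8 modules". Section 2.6-2.7 repeats the intention: "Potential impact of navigators will be assessed statistically prior to the main analyses and controlled for".

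The timing of the two rating scales is in section 2.8-2.9: "Perceived relationship with navigators is assessed at post-treatment with two measures". No other time is stated for them.

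Section 2.6-2.7 sets the outcome assessments for the treated groups at baseline, "post-treatment (within 2wks of completing the 8-module program); and 6-month follow-up". Section 2.16-2.18 defines the effect of treatment as the baseline-to-post change in FSDS-R and SIDI. The model described there does not list any navigator covariate.

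The one scheduled mid-treatment questionnaire contact is in section 2.6-2.7: "All participants will also be sent a mid-treatment link to an online question". It asks for free-text reactions and carries no empathy or alliance scale.

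**The concern.** The plan speaks of effects on outcomes, of impact and of control, all of which treat the navigator rating as a possible cause. A cause has to come before what it explains. Here the rating is made after the change, by the same woman who reports the change. If her distress fell, she may well think better of the person who supported her.

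Two things are at stake. The first is interpretation. A positive association could be taken as evidence about navigators, and section 2.8-2.9 says secondary outcomes will be used to refine the interventions. The second is adjustment. If a rating that responds to outcome is put into the model for CBT-O versus MBT-O, it removes part of the difference being estimated.

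**Working it through.** **Time order.** Setting the sections side by side:

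| Time | FSDS-R and SIDI | Empathy and alliance |
|---|---|---|
| Baseline | yes | no navigator relationship to rate yet |
| During modules 1-8 | no | none planned |
| Post-treatment | yes (primary change complete) | yes |
| 6 months | yes | none stated |

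For the primary change there is no rating that precedes it. Sections 2.3 to 2.18 contain no lagged analysis and no caution about direction. This fault needs no arithmetic, and the plan gives no figure of its own to reproduce.

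**Illustration of size.** Inputs: 90 rated women (section 2.10 expects 30 per arm after attrition, 3 × 30 = 90, with wait-list women later treated); alpha 0.05 from section 2.10, taken as two-sided because the sidedness is not stated; a correlation r between improvement and rating, assumed to be 0.2 to 0.4. Suppose the navigator has no effect and improvement alone produces r. By Fisher's z, the chance of a significant result is approximately Φ(atanh(r) × √(n − 3) − 1.96), with √87 = 9.327:

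- r = 0.2: 0.2027 × 9.327 − 1.96 = −0.07, giving 47%
- r = 0.3: 0.3095 × 9.327 − 1.96 = 0.93, giving 82%
- r = 0.4: 0.4236 × 9.327 − 1.96 = 1.99, giving 98%

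A simulation with 90 women gave 48% at r = 0.2, 81% at r = 0.3 and 5% at r = 0. With 75 women the formula gives about 40%, 75% and 95%. These are rates per test; two scales and two primary outcomes make four tests.

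**Adjustment.** Let Y be the change, with arm difference δ and within-arm SD 1, and let the rating be r·Y plus noise, scaled to within-arm SD 1. The within-arm slope of Y on the rating is r, and the arms differ in mean rating by r·δ. The adjusted arm difference is therefore δ − r × rδ = δ(1 − r²). The loss is 4% at r = 0.2, 9% at 0.3 and 16% at 0.4.

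**Six-month outcome.** Here the rating does come first, but an unadjusted analysis is still not clean. Let I and F be improvement from baseline at post-treatment and at 6 months, each with SD 1 and correlation ρ, and let the rating depend on I only. Then the covariance of the rating with F − I is rρ − r = −r(1 − ρ), the SD of F − I is √(2(1 − ρ)), and the correlation is −r√((1 − ρ)/2). With ρ assumed to be 0.6 to 0.8 and 90 women, a test with no navigator effect is significant in 9-13% of trials at r = 0.2, 14-24% at 0.3 and 22-39% at 0.4, and the association tends to be negative. Holding I fixed, the partial covariance is rρ − rρ = 0, so adjustment for the post-treatment level removes the artefact in this set-up.

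**The case against.** **The percentages are assumed.** They are the power of a correlation test at a chosen r. They show what follows if reverse causation is the whole story, not that it is. This stands. A reader might infer that the trial would often report a false navigator effect. The documents do not support that: they give no r and no evidence on direction.

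**The stakes are modest.** Aim 3 in section 1.2 concerns satisfaction and compliance, not whether navigators cause improvement. No section says the result will set navigator selection or training. The sentence at issue is a bias check that refers only to potential effects. This also stands, and it limits the point to an ancillary analysis and to any adjustment based on it.

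**Questionnaires are completed at all assessment points (section 2.8-2.9).** This does not supply the missing rating. At baseline there is no relationship to rate, and the next assessment point is post-treatment.

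**A mid-treatment rating can also reflect improvement.** This is correct. Study 1 in section 1.3 reports pre-post change after one module (desire d = 0.74, distress d = 0.41; 17 women, no control group), and FSDS-R and SIDI are not measured mid-treatment. An earlier rating reduces the problem without removing it.

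**Navigator minutes.** A reader might infer that the time log escapes the fault because it is not a post-treatment rating. Minutes accumulate during treatment and may respond to progress, so that cannot be claimed.

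**Conclusion.** The point holds for empathy and alliance in relation to the baseline-to-post change. As scheduled, the two directions of cause cannot be told apart, and a true navigator effect is neither shown nor excluded. That conclusion rests on the stated timing alone.

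The size is illustrative: about 47%, 82% and 98% significant results at assumed correlations of 0.2, 0.3 and 0.4, with 90 rated women and no navigator effect. The 4% to 16% shrinkage of the arm difference rests on the same assumed range and arises only if the ratings enter that model. A reader might infer that the primary efficacy analysis is compromised. The documents do not establish this, because the model in section 2.16-2.18 names no navigator covariate while two other sections promise control for navigator measures. The point is a cheap improvement to make before data collection, since a rating not taken during treatment cannot be recovered later.

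**What to change.** 1. Collect the two short scales during treatment as well, either on the existing mid-treatment link or with one of the questionnaires already given at the start of modules 2-8 (section 2.8-2.9). Use that rating when evaluating navigator effects, and state that it can still reflect early improvement because FSDS-R and SIDI are not measured at that time.
2. Report the relation of post-treatment ratings to baseline-to-post change as an association. Do not use it to claim, or to control for, a navigator effect on that change. Amend the two sentences that promise control, and make section 2.16-2.18 agree with them.
3. If post-treatment ratings are used to predict the 6-month outcome, adjust for the post-treatment FSDS-R or SIDI score, with baseline also in the model.

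Cost: a few more minutes of questionnaire and some missing mid-treatment ratings, since section 2.6-2.7 ties honoraria to the assessment points and that contact carries none. Items 2 and 3 need only a change of wording in the analysis plan.

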2.5 What are the planned inclusion/exclusion criteria?

Inclusion criteria: Cis and trans women, aged ≥ 19 y, of any sexual orientation. Women will not be excluded based on menopausal status, as prevalence of distressing sexual concerns is not age-related⁸⁸ and continues beyond menopause.⁸ In our other studies,⁸¹ mean age is ~ 42 y (22y-65y), so we also expect this age range here. Participants must:

- Be fluent in English (online materials delivered in English).
- Have consistent access to the internet, basic competency in using online platforms (self-report).
- Be in a committed, stable romantic relationship of at least 6 months⁸⁹ (because aspects of the interventions require partner participation). Partners may be of any gender.
- Meet telephone screening diagnostic criteria for Sexual Interest/Arousal Disorder.
- Be sexually active with a partner over the preceding 4 weeks (due to the sexual function outcome

measure), and willing to engage in sexual activity with their partner during the study.

Exclusion criteria: Women who:

- Have Sexual Dysfunction that is, in their estimation, attributable to another psychiatric diagnosis, the effect of a substance, a general medical condition (e.g., Multiple Sclerosis), or non-sexual conflict in the relationship, none of which are meant to be addressed by the proposed interventions.
- Poorly managed Anxiety or Mood Disorder (as per degree of life interference assessed at screening).
- Report suicidal ideation on the phone screen assessed using the Depression Anxiety Stress Scale.⁹²
- Report visual impairments that would make it difficult to read online materials.
- Are regularly using illegal recreational drugs, prescription narcotics, cannabis, or plan to change their medications over the course of the study.
- On assessment report plans to end their romantic relationship in the next 6 months.

2.6-2.7 What is the proposed duration of treatment? Proposed frequency and duration of follow up?

Assessment points: CONSORT²⁸ guidelines will be followed in terms of tracking number of participants recruited, randomized, and retained through assessment and treatment. For CBT-O and MBT-O groups, there are 3 assessment points (baseline; post-treatment (within 2wks of completing the 8-module program); and 6-month follow-up). For the wait-list group, there are 2 pre-treatment assessments at waiting period start and after randomization to treatment (4 assessment points; same online questionnaires). No treatment will be given to wait-list participants during this waiting period. However, after the second online questionnaires are complete, they will be randomized to either the CBT-O or MBT-O arm of eSense. All participants will also be sent a mid-treatment link to an online question that asks them to write freely about their reactions to the treatment to date. This is included to examine quality assurance of the intervention. To minimize attrition, honoraria will be linked to completion of each assessment point: \$30 for (each) baseline assessment, and \$40 at post-treatment and 6-month follow-up assessment points.

Protocol: All participation will be remote, requiring no in-person meetings. Prospective participants will contact the study coordinator at UBC via e-mail, then set up a phone screen for inclusion/exclusion criteria (Fig 1). Consent forms will be sent to prospective participants prior to the scheduled phone screen by the study coordinator. Women will be informed of the length of the intervention (8 modules; 8-12 wks), expectations for homework (1-2 hours/week), and the use of treatment navigators. After meeting the screening criteria, the study coordinator will send prospective participants a personalized link to a Qualtrics questionnaire battery. The first page of the questionnaires will be the e-consent form. Participants must read and electronically sign the consent form before they move on to the baseline questionnaires. The e-consent form will indicate that any questions/issues they raise in interactions with study staff that are worrisome (e.g., suicidal ideation) will automatically prompt the coordinator to contact them. Women who choose not to participate will be provided with other resources (websites, directories of sex therapists, books).

Prior to beginning eSense (Fig 1), participants will have an initial 15-30 min conversation via zoom with their assigned navigator, who will explain their role. These regularly scheduled⁶⁴ meetings have been found to significantly increase participation rates.^{83,93} Once treatment begins, navigators will schedule weekly 15-20 min sessions, and these will follow a structured outline that includes: 2-3 min general introduction, 10-15 min to check in on any concerns arising during completion of assigned homework, and 2-3 min to close and schedule their next session. Either the participant or the navigator can request a reassignment if there is not a good “fit.” This can happen at any time during the study by informing the study coordinator. Navigators will be: undergraduate psychology students; GPA>3.5; coursework in research methods, clinical psychology or human sexuality; and available to complete training (see letter of support from UBC Psychology chair, **Appendix**). They must be able to commit at least a full year to the project. Navigators will be asked to electronically sign the consent form. These signed consent forms will be stored securely on MS OneDrive. Only the study coordinator and co-investigators will have access

to the consent forms and it will not be stored with other data. Each navigator will be assigned a participant to work through all 8 modules. Navigators will be assigned up to 4 participants at the same time. Navigators can choose to be involved with either CBT-O or MBT-O, or both arms, if they feel comfortable. Their feedback to participants will largely be the same regardless of which arm the participant is in. A new coded variable will be included in the analysis to examine whether a navigator was assigned to an arm based on their preference (1) or no preference (0). Students will be interviewed by [name] to assess comfort with discussing sexual issues, interpersonal skills and ability for empathic listening. Potential impact of navigators will be assessed statistically prior to the main analyses and controlled for. CoA [name] will oversee navigator supervision.

We may conduct an exit interview for trans participants and participants who are not exclusively heterosexual so we can receive feedback on how our program could be improved for sexual orientation, gender, and sex-inclusivity. This exit interview would be optional for participants.

2.8-2.9 What are the proposed 1° and 2° outcome measures? How are they measured at follow up?

Our primary outcomes are clinical— sexual desire and sexual distress—and will be used to determine effect sizes needed for a future large RCT. Secondary outcomes will be used to refine the interventions. Questionnaires take ~30min and are completed at all assessment points using Qualtrics.

1° outcomes: Sexual distress will be measured by the Female Sexual Distress Scale-Revised⁹⁰ (FSDS-R), used extensively in women’s sexuality treatment outcome studies. Sexual desire will be measured by the The Sexual Interest and Desire Inventory (SIDI).

2° outcomes: Treatment satisfaction will be assessed with (i) two face-valid single item measures measured on through the eSense platform at the beginning of modules 2-8 and measures via Qualtrics a week after completing module 8 asking participants to rate helpfulness of content covered in the previous module, and ease of reading the content (1-10 scale); Research suggests a cut-off of 6.5/10 on these measures to indicate acceptable utility and clarity of content⁹⁴; (ii) qualitative feedback about website and homework assignments collected by treatment navigators; (iii) adapted Erectile Dysfunction Inventory of Treatment Satisfaction,⁹⁵ a widely used scale measuring satisfaction after treatment for erectile dysfunction. Perceived relationship with navigators is assessed at post-treatment with two measures: (i) Empathy subscale of the Barrett-Lennard Relationship Inventory,⁹⁶ a valid measure of perceived provider empathy that predicts outcomes in CBT⁹⁷; (ii) perceived navigator effectiveness with the Working Alliance Inventory, Short Form.⁹⁸ Treatment compliance will be measured by: (i) recording number of weeks and treatment sections completed⁹⁹; (ii) eSense website engagement and performance by Google analytics (e.g., page views, # visits/sessions, page views/visit, visit duration, unique/returning users); these metrics are recommended by the E-CONSORT guidelines as important for e-health intervention studies. The platform used to house eSense tracks views of a page and completion of the overall program, enhancing and complementing what analytics can provide; (iii) navigators will ask participants to rate homework completion on a Likert scale ranging from “did not attempt” to “successfully completed all assignments” weekly; (iv) having participants complete the Homework Rating Scale-II (HRS-II)¹⁰⁰ at the beginning of modules 2-8 on the eSense platform and then complete it again week via Qualtrics after completing module 8 to provide a comprehensive measure of experience with the homework; (v) measuring navigator adherence to study guidelines by coding a random 20% of Zoom sessions (participants will be informed of these recordings) for adherence (to be done by [name]’s trainee; no funding requested), using a previous adherence scale we have used.^{17,81} Sexual function will be measured using the total score of the Female Sexual Function Index,⁹¹ a validated self-report measure of sexual function.

2.10 What is the proposed sample size; justification for assumptions underlying power calculations?

Based on our findings,¹⁷ we expect large effect sizes for the main outcomes ($d=.8$ for FSFI and $d=1.05$ for FSDS-R) in the MBT-O arm. According to power analysis based on these two measures and two treatment

groups, 75 participants are needed to give us 90% power to discover a large size effect of our treatment at alpha level of .05 (PASS, 2019 Power Analysis and Sample Size Software (2019). NCSS, LLC. Kaysville, Utah, USA, [ncss.com/software/pass.](http://ncss.com/software/pass/)). Based on [name]'s work, we expect ~30% attrition so we will recruit 129 women (n=43 per arm) (control later randomized to treatment). After attrition, we expect to have n=30 in each arm.

